### 3.2.1 Endpoint for Secondary Objectives

- The 1-year relapse free survival rate is defined as the proportion of patients treated with dovitinib with no evidence of any remaining urothelial carcinoma tumors at 12 months of follow-up.

**NOTE:** Patients with residual non-invasive UC tumors with no component of carcinoma in situ (i.e. Ta, T1) at 3-month cystoscopy and TURBT are not considered relapses and will be permitted to continue on dovitinib therapy. If the subsequent 6-month cystoscopy/TURBT, and urine cytology shows no evidence of any remaining urothelial carcinoma in such patients, they will be considered a complete response. Patients with any component of carcinoma in-situ (CIS) at 3-month cystoscopy/TURBT will be considered relapses and will not continue on dovitinib therapy. Any non-invasive UC tumors (i.e. Ta, T1, Tis) at the 6-month or any subsequent cystoscopy/TURBT is considered relapsed disease. Similarly progression to invasive UC tumors (T2-T4) at any time point is also considered relapsed disease and patients will not continue on dovitinib therapy.

- The rate of progression to muscle-invasive stage for dovitinib is defined as the proportion of patients with clinical or pathologic progression to muscle-invasive stages (i.e. T2-T4) at any time point on study. Pathologic progression is assessed by histological finding at TURBT or cystectomy. Clinical progression is assessed by clinician's physical exam and findings on radiologic imaging as ordered per the treating physician's discretion.
- The 3- and 6-month partial response rates are defined as the proportion of patients treated with persistent but reduced T-stage tumors on post-therapy TURBT (i.e. T1 -> Ta; T1+Tis -> T1).
- Treatment related toxicity rates will be assessed by CTCAE v4.0.

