### **7.8 Replacement Policy**

Patients prematurely withdrawn within the first 3 months of therapy and prior to the first post-therapy cystoscopy with urine cytology and TURBT will be replaced. Patients prematurely withdrawn after their first post-therapy cystoscopy with urine cytology and TURBT will not be replaced.

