#### **7.10.11.2 Chemistry Studies**

Serum chemistries including BUN, creatinine, total bilirubin, ALT, AST, GGT, alkaline phosphatase, albumin, total protein, calcium, sodium, magnesium, potassium, phosphorous, glucose, LDH, amylase, and lipase will be assessed in each patient within 14 days of registration, at cycle 1 day 1, cycle 1 day 12, cycle 1 day 26, cycle 2 day 12, cycle 2 day 26, on day 26 of all subsequent cycles, and at the end of study treatment.

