#### **7.10.12.2 Relapse Free Survival (RFS)**

Relapse Free Survival (RFS) is defined as the time from study registration until the occurrence of any of the following relapse events:

1. Evidence of any component of CIS at 3-month cystoscopy/TURBT
2. Recurrent tumor  $\geq$  T2 at any time point
3. Recurrent tumor of any stage that occurs at or after the 6-month cystoscopy evaluation as assessed by bladder cystoscopy, TURBT, or urine cytology. Note: While not required as part of the study follow-up testing, positive urine FISH test (even if an isolated finding) at or after the 6-month study evaluations will be considered relapsed disease.
4. Documentation of metastatic urothelial carcinoma at any time point

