### **7.10.12.3 1-year Relapse Free Survival (1-yr RFS)**

1-year RFS is defined as the proportion of patients who do not fulfill any of the relapse definitions in section 7.10.11.2 one year after study registration.

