## **10 Statistical Methods and Data Analysis**

### **10.1 General Considerations**

Statistical analysis of this study will be the responsibility of the Department of Biostatistics at IUSM. Parameter estimates and relevant summary statistics will be reported for both efficacy and safety outcomes. Continuous variables will be summarized by means, medians, minima, maxima and standard deviations. Categorical variables will be summarized by frequencies and percentages. Missing data are expected to be rare. For patients that start therapy but do not make it to the primary endpoint evaluation, their 6-month status will be treated as not achieving CR. Consequently, our estimate of 6-month CR rate will be conservative. For secondary outcomes, missing data, if any, will not be imputed and complete-case analysis will be adopted. Additional exploratory analysis will be conducted when appropriate. Changes from the analysis plan will not require an amendment to the protocol unless it changes a significant feature in the protocol.

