#### **10.2.5 Efficacy Set**

The efficacy analysis set (EAS) consists of all patients who received at least one dose of study medication and had at least one post-treatment cystoscopy/TURBT and urine cytology performed.

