### **10.6.2 Secondary Objectives Statistical Considerations**

All secondary objectives are hypothesis generating in nature. One year RFS muscle-invasive progression, 3- and 6-month PR, and toxicity rates will be presented as rates and corresponding 90% Agresti-Coull CIs.

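### 1-year relapse-free survival is a time-to-event endpoint reported as a complete-case proportion, with no rule for censoring or for relapse-free death

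*Combined protocol and SAP*

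**What the plan says.** Section 7.10.12.2 makes RFS a duration: it "is defined as the time from study registration until the occurrence of any of the following relapse events". The four events are CIS at the 3-month evaluation, tumor of stage T2 or higher at any time, recurrence of any stage at or after the 6-month evaluation, and metastatic disease. Death is not listed.

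The 1-year rate is then defined twice as a proportion. Section 3.2.1 counts treated patients with "no evidence of any remaining urothelial carcinoma tumors at 12 months of follow-up". Section 7.10.12.3 uses "the proportion of patients who do not fulfill any of the relapse definitions in section 7.10.11.2 one year after study registration". The section number cited there is "7.10.11.2 Chemistry Studies"; the intended target is evidently 7.10.12.2.

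The analysis is also described in two ways. Section 10.6.2 groups 1-year RFS with muscle-invasive progression and partial response, and says that these and "toxicity rates will be presented as rates and corresponding 90% Agresti-Coull CIs". The Synopsis asks for the mean, median and standard deviation of 1-year RFS.

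On missing data, section 10.1 states: "For secondary outcomes, missing data, if any, will not be imputed and complete-case analysis will be adopted". For the primary endpoint the same section does set a rule: a treated patient who is not evaluated at 6 months counts as not in complete response. Section 10.7.1 plans univariate Cox regression for RFS, which needs censoring, but defines none.

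**The concern.** A complete-case proportion at 12 months treats patients unequally. Someone who relapses at month 3 and then leaves has a known outcome and stays in the denominator. Someone who is relapse-free at month 6 and then lost has an unknown outcome and is removed, along with the relapse-free time already observed. The observed group is therefore enriched for relapsers.

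Death is a second gap. The plan does not say whether a relapse-free death is an event, a censoring, a missing value or a success, and each gives a different rate from the same data.

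At stake is the trial's measure of durability. Section 1.1.4 motivates the study by noting that existing agents give remissions beyond one year in only 10-15% of patients, so readers will set the reported rate beside that range. The rule should be fixed before the data are seen.

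**Working it through.** The plan states no expected RFS, loss rate or death rate, so there is no plan figure to reproduce. Everything below except the sample size of 20 and the visit schedule is an assumption.

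**Inputs.** Visits at 3, 6, 9 and 12 months (section 7.10.7.1). Conditional relapse probabilities at these visits of shape 0.35/0.40/0.25/0.15, scaled so that the true 1-year RFS is S = 0.25. The shares of patients relapsing at each visit are then f = 0.349, 0.260, 0.098, 0.044. Annual loss r = 5, 10, 20 or 30%, at a constant hazard.

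**Non-informative loss.** The chance of still being followed at time t (years) is G(t) = (1-r)^t. The expected complete-case rate is

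S·G(1) / [S·G(1) + Σ f_i·G(t_i)].

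For r = 10%, G = 0.974, 0.949, 0.924, 0.900. The numerator is 0.25 × 0.900 = 0.225. The observed relapses are 0.340 + 0.246 + 0.090 + 0.040 = 0.716. The rate is 0.225/0.941 = 23.9%.

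| Annual loss | Complete-case rate | Bias (points) | Single 20-patient trials where it differs from Kaplan-Meier by at least 5 points |
|---|---|---|---|
| 5% | 24.5% | -0.5 | 1% |
| 10% | 23.9% | -1.1 | 4% |
| 20% | 22.7% | -2.3 | 13% |
| 30% | 21.4% | -3.6 | 27% |

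The last column comes from 200,000 simulated trials per row; 5 points is one patient of 20. At a true rate of 15% the complete-case rates are 14.6/14.2/13.4/12.5%, and at 35% they are 34.4/33.7/32.3/30.7%.

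**Relapse-free deaths, if treated as missing.** With annual mortality d, an RFS that counts death is 0.25 × (1-d). The complete-case rate is the formula above with r = d. At d = 5%: 24.5% against 23.8%, or +0.7 points. At d = 10%: 23.9% against 22.5%, or +1.4 points.

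**Informative loss.** Suppose patients who would relapse at the next visit drop out at m times the hazard of the others. Bias in points at 5/10/20/30% annual loss:

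| m | Complete case | Kaplan-Meier |
|---|---|---|
| 2 | -0.3/-0.6/-1.3/-2.0 | +0.4/+0.8/+1.6/+2.6 |
| 5 | +0.4/+0.9/+1.9/+3.0 | +1.5/+3.1/+6.7/+10.9 |

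**One dataset, N = 20.** Eight relapse at month 3, seven at month 6, two are lost relapse-free after month 6, one relapses at month 9, and two are free at month 12.

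- Complete case: 2/18 = 11.1% (90% Agresti-Coull interval 2.9-29.5%).
- Kaplan-Meier: (12/20) × (5/12) × (2/3) = 16.7% (90% log-log interval 5.0-34.3%).
- Worst and best case for the two lost: 2/20 = 10.0% and 4/20 = 20.0%.
- If both losses were deaths counted as events: 2/20 = 10.0%, against 11.1% if dropped.

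**The case against.** The case for leaving the plan alone has weight. Section 10.1 expects missing data to be rare. Section 7.7 calls for continued tumor assessments and telephone contact after the drug is stopped, and section 7.9 follows all patients for relapse. At 5-10% loss the bias is well under one patient, loss and death push in opposite directions, and the interval at 20 patients dwarfs both. The example is also unfavourable: it loses two of the five patients still relapse-free after month 6. With fixed visits a landmark proportion is a legitimate summary, and Kaplan-Meier does worse once patients near relapse are lost at roughly twice the rate of others or more. All of this stands. It limits the size of the problem and is the reason to show a range beside Kaplan-Meier. It does not supply the missing rules: follow-up effort reduces loss but does not say how to analyse what remains.

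Several stronger readings are tempting and are not supported.

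- A reader might infer that deaths will be dropped and the rate inflated. No section says so. Under section 3.2.1 a patient who died before month 12 could equally be counted as a failure.
- Read literally, section 7.10.12.3 would count lost or dead patients as relapse-free. The complete-case rule in section 10.1 makes that strained, so no size is claimed from it.
- The Efficacy Set requires that a patient "had at least one post-treatment cystoscopy/TURBT and urine cytology performed", and section 7.8 replaces "Patients prematurely withdrawn within the first 3 months of therapy and prior to the first post-therapy cystoscopy" assessments. This might seem to distort the rate. Under the stated rule it does not: a patient lost before month 3 has no observed relapse and is in neither numerator nor denominator.
- The wrong section number is clerical. Counting an isolated positive on an optional FISH test as relapse is a separate matter of event definition.

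**Conclusion.** The point holds as a minor one. The plan applies a complete-case proportion to a time-to-event endpoint, describes the summary differently in the Synopsis, and has no censoring or death rule. Under non-informative loss the rate is biased low by about 0.5 to 1 point at 5-10% annual loss and 2 to 4 points at 20-30%, for a true rate of 25%. If relapse-free deaths are handled as missing, the error is about 0.7 to 1.4 points upward at 5-10% mortality, relative to an RFS that counts death. The loss rates, death rates and relapse pattern are all assumed, and informative loss can reverse the direction of the first bias. The wording gaps are certain; the sizes are conditional.

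The primary endpoint has its own missing-data rule and is unaffected. Section 10.6.2 labels all secondary objectives hypothesis generating, and no decision rule uses this rate. It would be wrong to infer that the trial's main conclusion is at risk.

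**What to change.** Estimate 1-year RFS by Kaplan-Meier from the event times in section 7.10.12.2, with a 90% log-log confidence interval. Censor at the last disease evaluation and count death from any cause as an event. Beside it, show the rate with all lost patients taken as relapsed and with all taken as relapse-free, because Kaplan-Meier is biased up if patients near relapse are the ones lost. Put this single method in the Synopsis and sections 3.2.1, 7.10.12.3 and 10.6.2, and correct the cross-reference in 7.10.12.3 in the same edit.

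The cost is mostly wording. Relapse dates are already collected (section 7.7) and are needed for the Cox regression. Deaths on treatment and within 30 days of the last dose are already reported; later deaths may need one eCRF field. The rate may be slightly less favourable once deaths count, and the interval will be wide at 20 patients.

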### **10.2 Analysis Sets**

#### **10.2.1 Full Analysis Set**

The Full Analysis Set (FAS) comprises all patients to whom study treatment has been assigned. Patients will be analyzed according to the treatment they have been assigned to.

#### **10.2.2 Safety Set**

The Safety Set includes all patients who received at least one dose of study medication.

#### **10.2.3 Per-Protocol Set**

The Per-Protocol Set (PPS) consists of a subset of the patients in the FAS who do not have significant deviations from the inclusion/exclusion criteria and are compliant with the treatment plan.

#### **10.2.4 Pharmacokinetic Analysis Set**

The pharmacokinetic analysis set (PAS) consists of all patients who have evaluable pharmacokinetic (PK) data from post-treatment bladder tissue.

#### **10.2.5 Efficacy Set**

The efficacy analysis set (EAS) consists of all patients who received at least one dose of study medication and had at least one post-treatment cystoscopy/TURBT and urine cytology performed.

#### **10.2.6 Other Analysis Sets**

Correlative analysis sets will consist of all patient sets who have evaluable correlative data for each proposed correlative analysis. For instance, the plasma free FGFR3 mutation set will consist of all patients who have baseline plasma evaluable for FGFR3 mutation analysis.

### **10.3 Patient Demographics/Other Baseline Characteristics**

Demographic and other baseline data (including disease characteristics and FGFR3 mutation/over-expression status) will be summarized descriptively for all patients for the FAS.

### **10.4 Treatments (Study Drug, Concomitant Therapies, Compliance)**

Concomitant medications and significant non-drug therapies prior to and after the start of the study drug will be summarized for the safety set.

#### **10.4.1 Treatment Drug and Compliance**

Duration of treatment and compliance status will be tabulated for the safety set.

#### **10.4.2 Concomitant Therapies**

Concomitant medications and significant non-drug therapies prior to and after the start of the study drug will be summarized for the safety set.

### **10.5 Primary Objective**

The primary objective of the trial is to determine the 6-month complete response rate in BCG-refractory UC patients with FGFR3 mutant or over-expressing tumors treated with dovitinib.

#### **10.5.1 Primary Objective Statistical Considerations**

The 6-month complete response rate will be summarized by frequency and rate. The one-sided 90% confidence interval (CI) of Agresti-Coull type will be calculated for the rate.

### **10.6 Secondary Objectives**

#### **10.6.1 Key Secondary Objective(s)**

In addition to the study's primary objective, key secondary objectives include:

- To determine the 1-year relapse free survival rate.
- To determine the rate of progression to muscle-invasive stage (i.e. T2-T4).
- To determine 3- and 6-month partial response rate defined as a reduction in T-stage on post-therapy TURBT (i.e.  $T1 \geq Ta$ ;  $T1+Tis \geq Tis$ )
- To characterize treatment related toxicity rates assessed by CTCAE v4.0

### **10.6.2 Secondary Objectives Statistical Considerations**

All secondary objectives are hypothesis generating in nature. One year RFS muscle-invasive progression, 3- and 6-month PR, and toxicity rates will be presented as rates and corresponding 90% Agresti-Coull CIs.

### **10.6.3 Safety Objectives**

#### **10.6.3.1 Analysis Set and Grouping for the Analyses**

For all safety analyses, the safety set will be used.

The overall observation period will be divided into three mutually exclusive segments:

1. pre-treatment period: from day of patient's informed consent to the day before first dose of study medication
2. on-treatment period: from day of first dose of study medication to 30 days after last dose of study medication
3. post-treatment period: starting at day 31 after last dose of study medication.

#### **10.6.3.2 Adverse Events (AE)**

Summary tables for adverse events (AEs) have to include only AEs that started or worsened during the on-treatment period, the **treatment-emergent** AEs. However, all safety data (including those from the post-treatment period) will be listed and those collected during the pre-treatment and post-treatment period are to be flagged.

The incidence of treatment-emergent adverse events (new or worsening from baseline) will be summarized by system organ class and or preferred term, severity (based on CTC grades), type of adverse event, and relation to the study drug. Deaths reportable as SAEs and non-fatal serious adverse events will be listed by patient and tabulated by type of adverse event.

Specific safety event categories (SEC) will be considered. Such categories consist of one or more well-defined safety events which are similar in nature and for which there is a specific clinical interest in connection with the study treatment(s).

For each specified SEC, number and percentage of patients with at least one event part of the SEC will be reported.

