## **8 Safety Monitoring and Reporting**

### **8.1 Adverse Events**

#### **8.1.1 Definitions and Reporting**

An adverse event for the purposes of this protocol is defined as the appearance of (or worsening of any pre-existing) undesirable sign(s), symptom(s), or medical condition(s).

Abnormal laboratory values or test results constitute adverse events only if they induce clinical signs or symptoms, are considered clinically significant, or require therapy.

Adverse events will be assessed according to the Common Terminology Criteria for Adverse Events (CTCAE) version 4.0. If CTCAE grading does not exist for an adverse event, the severity of mild, moderate, severe, and life-threatening, or grades 1 - 4, will be used. CTCAE grade 5 (death) will not be used in this study; rather, this information will be collected and recorded in the Adverse Events eCRF as end of treatment or survival information.

Adverse events will be recorded from the time of consent and for at least 30 days after treatment discontinuation. All Adverse events considered related to trial medication will be followed until resolution, return to baseline, or deemed clinically insignificant, even if this occurs post-trial.

Abnormal laboratory values or test results occurring after signing the informed consent form constitute adverse events only if they induce clinical signs or symptoms, or require therapy, (e.g., any hematologic abnormality that requires transfusion or hematological stem cell support) or changes in study medication(s) are considered clinically significant and should be recorded on the Adverse Events eCRF under the signs, symptoms or diagnosis associated with them. In addition, isolated abnormal laboratory values that are considered clinically significant (e.g., cause study discontinuation or constitutes in and of itself a Serious Adverse Event) should be recorded on the Adverse Events eCRF.

The occurrence of adverse events should be sought by non-directive questioning of the patient (subject) during the screening process after signing informed consent and at each visit during the study. Adverse events also may be detected when they are volunteered by the patient (subject) during the screening process or between visits, or through physical examination, laboratory test, or other assessments. As far as possible, each adverse event should be evaluated to determine:

1. The severity grade (CTCAE grade 1-4)

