2. Causality to the adverse event (reasonable possibility that AE is related to dovitinib): (no, yes)
3. Its duration (start and end dates or if continuing at final exam)
4. Action taken with respect to study or investigational treatment (none, dose adjusted, temporarily interrupted, permanently discontinued, unknown, not applicable)

5. Outcome (not recovered/not resolved, recovered/resolved, recovering/resolving, recovered/resolved with sequelae, fatal, unknown)
6. Whether it is serious, where a serious adverse event (SAE) is defined as in Section 8.2.

**Unlike routine safety assessments, SAEs are monitored continuously and have special reporting requirements, see [Section 8.2](#).**

All adverse events should be treated appropriately. Treatment may include one or more of the following: no action taken (i.e. further observation only); study drug dosage adjusted/temporarily interrupted; study drug permanently discontinued due to this adverse event; concomitant medication given; non-drug therapy given; patient hospitalized/patient's hospitalization prolonged. The action taken to treat the adverse event should be recorded on the Adverse Event eCRF.

Once an adverse event is detected, it should be followed until its resolution or until it is judged to be permanent, and assessment should be made at each visit (or more frequently, if necessary) of any changes in severity, the suspected relationship to the study drug, the interventions required to treat it, and the outcome.

Disease progression should not be regarded or reported as an adverse event itself unless associated with a separate adverse event.

Whenever possible, a diagnosis should be reported instead of underlying signs and symptoms.

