## 8.2 Serious Adverse Events

### 8.2.1 Definitions

Serious adverse event (SAE) is defined as one of the following:

- Is fatal or life-threatening
- Results in persistent or significant disability/incapacity
- Constitutes a congenital anomaly/birth defect
- Requires inpatient hospitalization or prolongation of existing hospitalization, unless hospitalization is for:
  - Routine treatment or monitoring of the studied indication, not associated with any deterioration in condition (specify what this includes)
  - Elective or pre-planned treatment for a pre-existing condition that is unrelated to the indication under study and has not worsened since signing the informed consent
  - Treatment on an emergency outpatient basis for an event not fulfilling any of the definitions of a SAE given above and not resulting in hospital admission
  - Social reasons and respite care in the absence of any deterioration in the patient's general condition
  - Any SAEs that are expected due to the condition being treated, including if the SAE is a primary outcome measure, and whether there has been a clear agreement with regulators not to consider these as SAEs, provided the information is collected elsewhere
  - Is medically significant, i.e., defined as an event that jeopardizes the patient or may require medical or surgical intervention to prevent one of the outcomes listed above. Examples of such events include, but are not limited to, intensive treatment in an emergency room or at home for allergic bronchospasm; blood dyscrasias or convulsions not resulting in hospitalization; or the development of drug dependency or drug abuse.

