#### **8.2.2.2 Death and Immediately Life-Threatening Events**

Any death and immediately life-threatening event from any cause while a patient is receiving trial treatment on this protocol or up to 30 days after the last dose of trial treatment, or any death and immediately life-threatening event occurring more than 30 days after trial treatment has ended but which is felt to be treatment related must be reported **within one business day of discovery of the event**. All deaths must be reported primarily for the purposes of SAE reporting; however, deaths due unequivocally to progression are not SAEs.

Your local IRB should be notified and its reporting procedure followed. The completed SAE Reporting Form should be faxed to Hoosier Cancer Research Network **within one business day of discovery of the event**.

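### Section 10.6.3.2 tabulates only deaths that are reportable as SAEs, so an on-treatment death attributed to progression is collected but enters no summary table

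*Combined protocol and SAP*

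**What the plan says.** Four provisions of the combined protocol and SAP bear on how a death is handled.

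- **Analysis (section 10.6.3.2).** The only output defined for deaths is this: "Deaths reportable as SAEs and non-fatal serious adverse events will be listed by patient and tabulated by type of adverse event". The same section also promises a listing of every safety record, post-treatment records included, with those from outside the on-treatment period flagged.
- **Reporting (section 8.2.2.2).** Collection is broad. It covers "Any death and immediately life-threatening event from any cause while a patient is receiving trial treatment on this protocol", extends to 30 days after the last dose, and requires a report within one business day. The section then narrows the classification: "All deaths must be reported primarily for the purposes of SAE reporting; however, deaths due unequivocally to progression are not SAEs".
- **SAE definition (section 8.2.1).** The first criterion is "Is fatal or life-threatening". No exception for progression is attached to it.
- **Adverse event recording (section 8.1.1).** "CTCAE grade 5 (death) will not be used in this study; rather, this information will be collected and recorded in the Adverse Events eCRF", under end-of-treatment or survival information. Also: "Disease progression should not be regarded or reported as an adverse event itself unless associated with a separate adverse event".

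The section headed Blinding states that neither patient nor investigator is blinded.

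**The concern.** A safety summary normally shows how many treated patients died during treatment and shortly after it, whatever the cause, and then divides that number by cause. Here the division comes first. Cause decides whether a death is an SAE, and SAE status decides whether it is tabulated. A reader of the tables alone would see a count of deaths not attributed to progression and could take it for the count of all deaths.

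This matters more in a single-arm, open-label trial. There is no control arm in which the same rule would remove a similar number of deaths, and the documents describe no independent review of cause of death. Treatment-related toxicity is also a stated secondary objective (section 3.2), so the safety tables are a main product of the study.

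**Working it through.** The plan gives no figure for deaths, so there is nothing to reproduce. The check follows one hypothetical case through the text: a patient who dies between the first dose and 30 days after the last dose, with the death attributed clearly to progression.

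1. **Is it collected?** Yes. Section 8.2.2.2 requires a report whatever the cause, and section 8.1.1 puts the information on the Adverse Events eCRF.
2. **Is it an SAE?** Under the first criterion of section 8.2.1, yes. Under the specific statement in section 8.2.2.2, no. If the specific statement governs, the death is not an SAE.
3. **Is it in the death table of section 10.6.3.2?** No. That table is limited to deaths reportable as SAEs.
4. **Is it in the treatment-emergent adverse event tables?** Not as a death. Progression alone is not an adverse event (section 8.1.1). If a separate, non-fatal event accompanied the progression, that event is tabulated, but at grade 4 at most because grade 5 is not used. Section 8.1.1 records a fatal outcome for adverse events, but section 10.6.3.2 plans no summary by outcome.
5. **Is it in another safety output?** No. The others are the specific safety event categories (10.6.3.2), laboratory tables (10.6.3.3), and ECG and vital signs (10.6.3.4).
6. **Is it in an efficacy output?** No. There is no overall survival endpoint, and death is not among the four relapse events that define RFS in section 7.10.12.2.
7. **Is it in a listing?** Probably, through the general listing of safety data in section 10.6.3.2. A listing gives no count or rate.

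The case is collected and probably listed, but tabulated nowhere.

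**Size.** The sample size is 20 (section 10.8). One untabulated death is 1/20 = 0.05, or 5 percentage points of an all-cause death proportion. Early withdrawals are replaced (section 7.8), so the Safety Set may exceed 20, and each death would then weigh slightly less. The documents give no expected number of such deaths. I assume none or one, a range of 0 to 5 percentage points.

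**The case against.** The strongest reply is that nothing is lost. Every death up to 30 days after treatment must be reported within one business day and recorded on the Adverse Events eCRF, and all safety data are listed. With about 20 patients, a by-patient listing lets a careful reader find each death. The coordinating network reviews events that need expedited reporting, and summaries go to a monitoring committee at least twice a year (section 8.5, although that section also says no formal committee will be used). Sections 8.2.1 and 8.2.2.2 can be read as a general rule with a specific exception. All of this stands, and it limits the point to a missing summary.

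Three stronger readings are tempting, and the documents do not support them.

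- **A reader might infer that a fatal drug reaction could drop out of the tables because the tumor had also progressed.** As written, it would not. The exception in section 8.2.2.2 requires that progression be the unequivocal cause. A fatal hepatic injury, for example, is a separate adverse event, is an SAE under section 8.2.1, and must be reported regardless of causality under section 8.2.2. It would be tabulated unless the rule were misapplied.
- **A reader might infer that the treating investigator alone decides.** The documents do not say who makes the judgement. That it rests with the site is an inference, since the site completes the SAE form and no adjudication is described.
- **A reader might infer that a planned confidence interval is understated.** The 90% Agresti-Coull intervals in section 10.6.2 are for toxicity rates, which the objective defines as treatment related. A death due to progression is not in them under either wording.

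**Conclusion.** The point holds as a reporting gap of low severity. The only death table leaves out deaths attributed to progression, no other summary restores them, and inclusion turns on a judgement of cause made without blinding or described adjudication. Sections 8.2.1 and 8.2.2.2 also differ on whether such a death is an SAE, so two programmers could build different death tables from the same plan.

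The size is modest: 5 percentage points of an all-cause death proportion for each such death among 20 patients, with none or one assumed. That assumption rests on entry being limited to Ta, T1 or Tis disease, with muscle-invasive and metastatic disease excluded (sections 5.1 and 5.2), and on treatment ending at relapse (section 7.6). The conclusion also assumes that the specific statement in section 8.2.2.2 overrides the general definition. If the general definition governs, the on-treatment gap closes, but the plan does not say so. The primary analysis, the sample size and the planned intervals are unaffected.

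**What to change.** - **Section 10.6.3.2.** Replace the restriction to SAE-reportable deaths with a rule to list and tabulate all deaths in the Safety Set, from any cause, from first dose to 30 days after last dose, by attributed cause. This matches the on-treatment period in section 10.6.3.1 and makes the total independent of attribution, while still showing the attribution.
- **Later deaths.** List any that become known separately, with a note that their collection is incomplete. Beyond 30 days, section 8.2.2.2 requires only deaths felt to be treatment related, and follow-up under section 7.9 ends at relapse or 12 months after the last dose. A complete count of later deaths would need added data collection, which is not proposed here.
- **Sections 8.2.1 and 8.2.2.2.** Reconcile them so that the SAE status of a progression death is stated once, the same way in both places.

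The cost is one extra table and some wording, using data already collected for on-treatment deaths. The reported death count may be slightly less favourable.
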